7.0 DISCONTINUATION OF STUDY INTERVENTION AND PARTICIPANT DISCONTINUATION/WITHDRAWAL

7.1 Discontinuation of Study Intervention

Not applicable as this is a single dose study.

7.2 Contraindications to Subsequent Study Interventions Administration

Not applicable as this is a single dose study.

7.3 Participant Discontinuation/Withdrawal from the Study

The participant's parent(s)/LAR(s) may withdraw the participant from the study at any time or the investigator may decide to withdraw a participant for safety, compliance, administrative, or other reasons.

A participant is considered a "withdrawal" from the study when no study procedure has occurred, no follow-up has been performed, and no further information has been collected for this participant from the date of withdrawal/last contact.

From an analysis perspective, a study "withdrawal" refers to any participant who was not available for the concluding contact planned in the protocol.

All data and samples collected up to and including the date of withdrawal of/last contact with the participant parent(s)/LAR(s) will be included in the study analyses.

The primary reason for study withdrawal shall be documented in the eCRF. Examples of the reasons may include:

- Adverse event requiring expedited reporting to IQVIA (see Appendix 3 for the details regarding such events)
- Unsolicited nonserious AE
- Solicited AE
- Withdrawal by the participant's parent(s)/LAR(s) but not due to AE^{*}
- Migrated/moved from the study area
- Lost to follow-up
- Study termination
- Other (specify)

*If a participant is withdrawn from the study because the participant's parent(s)/LAR(s) have withdrawn consent and the reason for withdrawal was provided, the investigator must document this reason in the eCRF.

Participants who are withdrawn from the study because of SAEs/AEs must be clearly distinguished from participants who are withdrawn for other reasons. The investigators should follow-up with parent(s)/LAR(s) of participants who are withdrawn from the study as a result of an SAE/AE until the event is resolved (see Appendix 3 for details regarding follow-up for AEs).

7.4 Lost to Follow-up

A participant will be considered lost to follow-up if he/she fails to return for scheduled visits and is unable to be contacted by the study center staff.

Refer to the SRM for a description of actions to be taken before considering the participant lost to follow-up.
8.0 STUDY ASSESSMENTS AND PROCEDURES

Study procedures and their timing are summarized in the Schedule of Activities (SoA) (Section 1.3). Protocol waivers or exemptions are not allowed.

Immediate safety concerns should be discussed with IQVIA immediately upon occurrence or awareness to determine if the participant should continue or discontinue study intervention.

Adherence to the study design requirements, including those specified in the SoA, is essential and required for study conduct.

All screening evaluations must be completed and reviewed to confirm that potential participants meet all eligibility criteria. The investigator will maintain a screening log to record details of all participants screened and to confirm eligibility.

The SRM provides the investigator and study center personnel with detailed administrative and technical information that does not impact the participant safety.

8.1 Immunogenicity Assessments

8.1.1 Biological samples

An overall volume of ~10 mL (5 mL each at Visit 1 and Visit 3) per participant will be collected during the entire study period.

Biological samples will be used for research planned in the protocol and for purposes related to the improvement, development and quality assurance of the laboratory tests described in this protocol.

Findings in this study or future studies may make it desirable to use samples acquired in this study for research not planned in this protocol. In this case, all participants will be asked to give consent to allow GSK or a contracted partner, to use the samples for further research. The further research will be subject to prior Institutional Review Board (IRB)/Independent Ethics Committee (IEC) approval, if required by local legislation.

Information on further research and its rationale can be obtained from GSK.

Sample testing will be done in accordance with the recorded consent of the participant's parent(s)/LAR(s).

By default, collected samples will be stored for a maximum of 20 years. This storage period begins when the last participant performs the last study visit. This timeline can be adapted based on local laws, regulations or guidelines requiring different timeframes or procedures. In all cases, the storage period should be aligned with participant's consent. These additional requirements must be formally communicated to, discussed and agreed with GSK.

8.1.2 Laboratory Assays

All laboratory testing will be performed as indicated in Table 9 at GSK laboratory or in a laboratory designated by GSK. The assay to measure immune responses to measles, mumps, and rubella are qualified for use in this Phase II study and will be validated for future Phase III studies in the MMRVNS Clinical Development Program. The assay to measure immune response to varicella is validated and used in other GSK Clinical Development Programs.

Table 9Laboratory Assays

Assay type	System	Component	Method
Humoral Immunity (Antibody		Anti-measles Ab IgG	Multiplex Luminex
determination)	Serum	Anti-mumps Ab IgG	based Immuno Assay
		Anti-rubella Ab IgG	
		Anti-gE Ab IgG	ELISA

Abbreviations: Ab = antibody; ELISA = enzyme-linked immunosorbent assay; gE = glycoprotein E; IgG = immunoglobulin G

8.1.3 Immunological Correlates of Protection

For measles, mumps, and rubella, there is no established correlate of protection with the anti-measles, -mumps, -rubella Multiplex Luminex based Immuno assay to be used in this study.

The following seroresponse threshold values are proposed by GSK as endpoint defining active immunization offering clinical benefit:

- 67 milli international units (mIU)/mL for anti-measles antibodies
- 296 arbitrary units (AU)/mL for anti-mumps antibodies
- 17 international units (IU)/mL for anti-rubella antibodies

For varicella, there is no established correlate of protection with the anti-glycoprotein E (gE) enzyme-linked immunosorbent assay (ELISA) assay to be used in this study. An anti-gE antibody threshold of 300 mIU/mL is accepted by the Food and Drug Administration as endpoint defining active immunization offering clinical benefit.

The investigator will be provided with the list of participants who do not achieve the pre-specified seroresponse threshold criteria in a timely manner (no later than 12 months after the last sampling date of the last participant enrolled).

At the end of the study, participants who would not achieve the pre-specified seroresponse threshold criteria will be offered re-vaccination at the investigator's discretion and depending on local recommendations, with a dose of licensed MMRV, MMR or varicella vaccine, depending on the antigen(s) for which the seroresponse threshold was not achieved.

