# 3.3. Changes to Analysis from Protocol

The seroresponse thresholds for anti-measles antibodies and anti-rubella antibodies offering clinical benefit were updated and communicated to the FDA. The SAP was updated with the new thresholds but the Protocol was not

Analysis Plan Page 24 of 57

updated.

The assay cut-offs were updated during assay validation for anti-mumps antibodies and anti-rubella antibodies. The SAP was updated but the Protocol was not updated.

The distribution of antibody concentrations for each antigen display using reverse cumulative curves will no longer be for the sub-cohort of initially seronegative participants, due to an expectation of a low number of participants in this sub-cohort.

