# 6.6. Common Calculations

Geometric Mean Concentration (GMC):

Distributions of antibodies are generally skewed to the right (Nauta, 2010). Therefore, prior to any statistical analysis that assumes normally distributed observations, antibody titers or concentrations will be log10-transformed.

Analysis Plan Page 31 of 57

GMCs and their 95% CI are computed by exponentiating (base 10) the least squares mean and 95% CI of the log10 concentrations.

The GMC will be calculated using the following formula:

$$10^{\left(\frac{\sum_{i=1}^{n}\log 10(t_i)}{n}\right)}$$

Where  $t_1, t_2, ..., t_n$  are n observed immunogenicity concentrations.

Concentration below assay cut-off (i.e., <lower limit of quantification or < LLOQ) will be replaced by half the assay cut-off (LLOQ/2) for the purpose of GMC computation. Concentrations above the upper limit of quantification (ULOQ) will be replaced by the ULOQ value.

Seroresponse rate for measles, mumps and rubella is defined as the percentage of participants for whom the postdose antibody concentration (Day 43), as measured by the anti-measles, -mumps, -rubella Multiplex Luminex based Immuno assay is  $\geq$  to the following threshold values:

- 116 mIU/mL for anti-measles
- 296 AU/mL for anti-mumps
- 24 IU/mL for anti-rubella

Seroresponse rate for varicella is defined as the percentage of participants for whom the post-dose anti-gE antibody concentration (Day 43) is ≥300 mIU/mL.

Analysis Plan Page 32 of 57

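### The investigator list and re-vaccination offer in Protocol 8.1.3 still rest on measles 67 mIU/mL and rubella 17 IU/mL, which SAP v5.0 replaced with 116 and 24

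*Protocol*

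**What the plan says.** Protocol 8.1.3 does two things in the same section. It sets seroresponse thresholds: "67 milli international units (mIU)/mL for anti-measles antibodies", "17 international units (IU)/mL for anti-rubella antibodies", 296 AU/mL for mumps and 300 mIU/mL for anti-gE. It then ties two participant-level actions to those thresholds:

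- A list for sites: "The investigator will be provided with the list of participants who do not achieve the pre-specified seroresponse threshold criteria". It is due within 12 months of the last participant's last sample.
- An offer of a licensed vaccine at the end of the study: "participants who would not achieve the pre-specified seroresponse threshold criteria will be offered re-vaccination". The offer is subject to the investigator's judgement and local recommendations, and the vaccine depends on which antigen was missed.

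Protocol 9.3.3.1 repeats the same four values for the seroresponse endpoints.

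SAP v5.0, section 6.6, defines seroresponse with "116 mIU/mL for anti-measles" and "24 IU/mL for anti-rubella", keeping 296 for mumps and 300 for anti-gE. SAP 3.3 explains that the measles and rubella thresholds "offering clinical benefit were updated and communicated to the FDA". On the protocol, it says: "The SAP was updated with the new thresholds but the Protocol was not". SAP section 1 still names protocol Amendment 1.0 of 15 March 2023 as its basis.

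**The concern.** SAP 3.3 openly records the change to the seroresponse analysis, and that is not in dispute. The difficulty is that the same thresholds also decide which children are reported to their investigator and considered for another dose. That rule is a protocol procedure, and SAP 3.3, which covers changes to the analysis, does not mention it.

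Both documents attach the same meaning to the thresholds: the antibody level at which immunization is taken to give clinical benefit. The sponsor has raised that level for two antigens, but the printed rule that acts on it keeps the lower values. Both changes go upward, so the mismatch runs one way. Some children would be counted as non-responders in the report without their investigator being told or a dose being offered. An investigator can use discretion only for children who appear on the list.

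**Working it through.** There is no planned figure to reproduce. The check compares the thresholds and follows each rule to its result.

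| Antigen | Protocol 8.1.3 and 9.3.3.1 | SAP v5.0, 6.6 | Difference | Ratio | log10 ratio |
|---|---|---|---|---|---|
| Measles (mIU/mL) | 67 | 116 | 116 − 67 = 49 | 116/67 = 1.73 | 0.238 |
| Rubella (IU/mL) | 17 | 24 | 24 − 17 = 7 | 24/17 = 1.41 | 0.150 |
| Mumps (AU/mL) | 296 | 296 | 0 | 1 | 0 |
| Anti-gE (mIU/mL) | 300 | 300 | 0 | 1 | 0 |

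**Classification by Day 43 result**

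| Result | SAP 6.6 | Protocol 8.1.3 as printed |
|---|---|---|
| Measles below 67, or rubella below 17 | Non-responder | Listed, dose offered |
| Measles 67 to below 116, or rubella 17 to below 24 | Non-responder | Not listed, no offer for that antigen |
| Measles 116 or more, or rubella 24 or more | Responder | Not listed, no offer for that antigen |

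The two documents disagree only in the middle row.

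**Sequence of versions.** The SAP Modification History shows that v3.0 changed the seroresponse values after a protocol update. In v5.0 they changed in the SAP alone. From Amendment 1.0 (15 March 2023) to SAP v5.0 (9 December 2024) is 635 days: 366 to 15 March 2024, plus 269.

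**Why no count is given.** The documents state no expected Day 43 GMC or seroresponse rate. The share of children in the gap is

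Φ((log10 new − log10 GMC)/SD) − Φ((log10 old − log10 GMC)/SD).

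Protocol 9.5 gives 0.45 on the log10 scale. It calls this a standard error, but its 1.25-fold half-width reproduces if 0.45 is read as an SD: 10^(1.96 × 0.45 × √(2/160)) = 1.255. With SD 0.45, and the GMC assumed to be a multiple of the new threshold:

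| Assumed GMC / new threshold | Measles share in gap | Rubella share in gap |
|---|---|---|
| 2 | 0.1364 | 0.0935 |
| 5 | 0.0416 | 0.0305 |
| 10 | 0.0102 | 0.0078 |
| 20 | 0.0016 | 0.0013 |

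The result moves from more than one child in ten to fewer than two in a thousand on the assumed GMC alone. The table shows only that the documents do not determine a count.

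**The case against.** The strongest reply is that this is a disclosed version difference with no demonstrated consequence. Sites do not apply 67 or 17 themselves; they are handed a list. Protocol Table 12 gives laboratory assessments to the sponsor, which adopted 116 and 24 and may build the list from them. The sentences about the list and the offer contain no numbers, so the criteria they invoke could be read as the current SAP values. The Study Reference Manual, which is not among the documents, may already settle the matter.

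Clinically, little may turn on it. Protocol 8.1.3 says no correlate of protection is established for these assays. The offer is discretionary. Each vaccinated child has had a qualifying first dose (Protocol 5.1) plus the study dose, so another would be a third measles-, mumps- and rubella-containing dose. Which antibody level should prompt it is a clinical choice.

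Much of this stands, and it is why the point is minor. It is a mismatch between documents, not a fault in any analysis, and current practice may already be right. What does not stand is the inference that nothing needs correcting. The natural reading of 8.1.3 is the values printed directly above the rule, and 9.3.3.1 gives the same ones. If the wording can be read either way, it still needs clarifying. Protocol 8.0 also describes the manual as administrative and technical material without bearing on participant safety, which makes it a weak place to override a printed protocol value. If the sponsor deliberately keeps the lower values for individual offers, neither document says so.

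**Conclusion.** The concern holds, at minor severity. As printed, the list and re-vaccination offer use superseded thresholds for measles (67 against 116 mIU/mL, 1.73-fold) and rubella (17 against 24 IU/mL, 1.41-fold). Mumps and anti-gE are consistent. This rests on reading the rule in 8.1.3 as referring to the values in the same section, and on no unseen document having redirected it. Confidence is high for the textual mismatch. How many children it touches is unknown and could be close to none. No endpoint, analysis set or model changes.

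**What to change.** State, by protocol amendment or documented clarification to investigators, that the list and offer in Protocol 8.1.3 use the SAP 6.6 thresholds: measles 116 mIU/mL and rubella 24 IU/mL, with mumps 296 AU/mL and anti-gE 300 mIU/mL unchanged. If a list has already gone out at 67 and 17, reissue it.

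The text is one line. An amendment needs ethics approval before implementation, and health authority approval if substantial (Protocol 10.1.1). A clarification is lighter, but the sponsor should confirm that it is an acceptable way to supersede values printed in an approved protocol. The practical downside is that a few more children may be offered a licensed dose, which for measles, mumps and rubella would be their third. No analysis has to be redone.

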8.2 Safety Assessments

8.2.1 **Pre-intervention Administration Procedures**

8.2.1.1 Collection of Demographic Data, Medical/Vaccination History

Demographic data such as age in years, sex, race, and ethnicity will be collected from each participant. Race and ethnicity will be collected as GSK seeks to have diverse clinical study participation (to see if the study vaccine works in all populations). Medical history should be collected, and it should be verified that none of exclusion criteria related to medical and vaccination history (see Section 5.2) are met. Prior vaccination history with respect to measles-, mumps-, rubella-, and varicella-containing vaccines should be obtained and recorded in the eCRF.

8.2.1.2 Checking Contraindications, Warnings, and Precautions to Intervention Administration

The body temperature of each participant will be measured prior to the study intervention administration. GSK will provide the study center with the temperature measuring device which are standard devices validated by GSK's Quality Assurance Team to ensure consistency in the data across study centers. If the participant has a fever (defined as temperature \geq 38.0°C (100.4°F) regardless of the location of measurement) on the day of the intervention administration, or other health conditions that can be considered temporary, Visit 1 can be rescheduled (see Section 5.5) as long as the eligibility criteria are still met (see Section 5.1 and Section 5.2).

8.2.2 Physical Examinations

A routine physical examination as per local standard of care will be performed for each participant on Day 1. If the investigator determines that the participant's health on the day of the study intervention administration temporarily precludes dosing, the visit will be rescheduled. Refer to Section 5.5 for the list of criteria for the temporary delay of study intervention administration.

8.2.3 Clinical Safety Laboratory Tests

No clinical safety laboratory tests are planned per protocol. Clinical safety laboratory tests may be performed at the investigator's discretion if deemed necessary in case of safety concerns.

8.2.4 Safety Monitoring

An IDMC comprising of clinical experts and a biostatistician will provide safety oversight during the active vaccination period, through unblinded review of the cumulative safety data. The first IDMC review meeting is planned after Day 43 safety follow-up of the first 200 vaccinated participants (approximately 50 in each group, considering pooled MMRV groups) is completed. A subsequent IDMC review meeting is planned during the study, after Day 43 safety follow-up of 400 participants is completed. The details of the review will be described in an IDMC charter.

In addition to the planned IDMC meetings, monthly SRT review by GSK will occur till the first 200 vaccinated participants complete the Day 43 safety follow-up, to monitor cumulative, blinded safety data (including serious and nonserious AEs). The blinded safety data review by the SRT may trigger an emergency ad-hoc IDMC review.

Solicited administration site events in terms of injection site redness, pain, and swelling; and solicited systemic events in terms of drowsiness, loss of appetite, fever, measles/rubella-like rash, varicella-like rash and other rash (not measles/rubella-like rash or varicella-like rash) will be collected. Unsolicited AEs, including SAEs will be encoded according to the latest version of the Medical Dictionary for Regulatory Activities dictionary.

8.3 Adverse Events, Serious Adverse Events, and Other Safety Reporting

8.3.1 Time Period and Frequency for Collecting AE and SAEs and Other Safety Information

The definitions of an AE or SAE are provided in Appendix 3.

Collection of AEs starts on the day of the study intervention (Day 1) up to Day 43 unless the AE leads to study discontinuation. Collection of SAEs starts the day of the study intervention (Day 1) and up to study end (Day 181) unless the SAE leads to study discontinuation. The frequency for collection of AEs and SAEs is shown in the SoA (Section 1.3).

8.3.2 Method of Detecting AEs and SAEs

The methods for detecting and recording AEs and SAEs, and the assessment of AE/SAE intensity, causality and outcome are provided in Appendix 3.

The study center staff should instruct participants' parent(s)/LAR(s) on how to report signs and symptoms (e.g., pain) in the individual participant. They will be instructed to report both specific and non-specific symptoms.

Care will be taken not to introduce bias when detecting AEs and SAEs. Open-ended and non-leading verbal questioning of the participants' parent(s)/LAR(s) is the preferred method to inquire about AE occurrences. Examples of the open-ended questions include "Did your child have any significant medical problem since the last study visit?" The study center staff should refrain from detailed questions, e.g., "Since the last visit, has your child experienced any of the following (checklist)?"

After the initial AE/SAE report, the investigator is required to proactively follow each participant at subsequent visits/contacts. All SAEs will be followed until resolution, stabilization, the event is otherwise explained, or the participant is lost to follow-up. Further information on follow-up procedures is provided in Appendix 3.

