10.3.4 Unsolicited Adverse Events

An unsolicited AE is an AE that was either not included in the list of solicited events or could be included in the list of solicited events but with an onset outside the specified period of follow-up for solicited events. Unsolicited AEs must have been communicated by a participant's parent(s)/LAR(s) who has signed the informed consent. Unsolicited AEs include both serious and nonserious AEs.

Potential unsolicited AEs may be medically attended (i.e., symptoms or illnesses requiring a hospitalization, or an emergency room visit, or visit to/by a health care provider). The participant's parent(s)/LAR(s) will be instructed to contact the site as soon as possible to

report medically attended event(s), as well as any events that, though not medically attended, are of participant's parent(s)/LAR(s)' concern. Detailed information about reported unsolicited AEs will be collected by qualified site personnel and documented in the participant's records.

Unsolicited AEs that are not medically attended or perceived as a concern by the participant's parent(s)/LAR(s) will be collected during an interview with the participant's parent(s)/LAR(s) and by review of available medical records at the next visit.

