All solicited administration site events that occur during 4 days (Day 1 to Day 4), and solicited systemic events that occur during 4 days (Day 1 to Day 4; for drowsiness and loss of appetite) or 43 days (Day 1 to Day 43; other solicited systemic events) following administration of the study intervention, must be recorded into the eDiary/personal electronic device app, irrespective of intensity. Unsolicited events occurring from Day 1 to Day 43 and SAEs occurring up the end of the study should be recorded into the appropriate section of the eCRF, irrespective of intensity or whether or not they are considered vaccination related.

Follow-up of AEs and SAEs

After the initial AE/SAE or any other event of interest for the study, the investigator is required to proactively follow each participant at subsequent visits/contacts. All SAEs will be followed until the event is resolved, stabilized, or otherwise explained or the participant is lost to follow-up.

Other nonserious AEs must be followed until the last contact or until the participant is lost to follow-up.

Follow-up During the Study

AEs documented at a previous visit/contact and defined as not recovered/not resolved or recovering/resolving will be reviewed at subsequent visits/contacts until the last visit/contact of the participant.

If the participant dies during participation in the study or during a recognized follow-up period, IQVIA will be provided with any available post-mortem findings, including histopathology.

Follow-up After the Participant is Discharged from the Study

The investigator will provide any new or updated relevant information on previously reported SAE to IQVIA using electronic Expedited AE Report as applicable. The investigator is obliged to perform or arrange for the conduct of supplemental clinical examinations/tests and/or evaluations to elucidate the nature and/or causality of the AE or SAE as fully as possible.

Updating of SAE Information After Removal of Write Access to the Participant's eCRF

When additional SAE information is received after removal of write access to the participant's eCRF, new or updated information should be recorded on the appropriate paper report, with all changes signed and dated by the investigator. The updated report should be faxed to IQVIA as described within the timeframes specified in Section 8.3.1.

Events Requiring Expedited Reporting to IQVIA:

SAE(s) throughout the study

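### The only example adverse-event question in protocol section 8.3.2 carries a severity filter that conflicts with the interview's purpose, so minor unsolicited AEs may be under-collected

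*Protocol*

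**What the plan says.** Protocol section 8.3.2 sets the interviewing approach: "Open-ended and non-leading verbal questioning of the participants' parent(s)/LAR(s) is the preferred method to inquire about AE occurrences". It continues with "Examples of the open-ended questions include" and then prints a single question: "Did your child have any significant medical problem since the last study visit". On prompting by symptom list it says: "The study center staff should refrain from detailed questions". Earlier in the section, on how parents are to be instructed, it says: "They will be instructed to report both specific and non-specific symptoms".

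Section 10.3.4 divides unsolicited AEs by route. Parents are to contact the site promptly to "report medically attended event(s), as well as any events that, though not medically attended, are of participant's parent(s)/LAR(s)' concern". For the rest, "Unsolicited AEs that are not medically attended or perceived as a concern by the participant's parent(s)/LAR(s) will be collected during an interview" with the parent, supplemented by a review of whatever medical records are available at the next visit.

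Section 10.3.10 says that unsolicited events from Day 1 to Day 43 "should be recorded into the appropriate section of the eCRF, irrespective of intensity or whether or not they are considered vaccination related". Section 10.3.6 defines grade 1 as an event that the child tolerates easily and that does not disturb daily activity, so such an event is recordable.

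The percentage of participants with unsolicited AEs in Days 1-43 is a secondary endpoint (protocol section 3.0, Table 6, and section 9.3.3.2). The SAP tabulates it by system organ class and preferred term, and again by country (SAP section 16.1.2).

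**The concern.** The interview is the main route for events that the parent did not find worrying and did not take to a doctor. The one question offered as a model asks the parent to report only what is significant. The filter therefore falls on the class of event that the interview exists to collect.

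At stake is the completeness of a stated secondary endpoint, mostly at grade 1. The SAP also summarises, by severity including mild, unsolicited events that match a solicited term but start after the solicited period (SAP section 16.1.1, Table H). Mild drowsiness starting on Day 5, for example, reaches that table only through unsolicited reporting. Protocol section 4.4 says the study is meant to support licensure, so absolute AE percentages matter even though section 9.1 makes every analysis descriptive.

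**Working it through.** The documents state no figure that can be reproduced for this point: no expected unsolicited AE rate, no share of minor events and no capture rate. The check is a comparison of the text, followed by an illustration on assumed inputs.

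**Comparison of the text**

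| Step | Where | What follows |
|---|---|---|
| Which events does the parent volunteer? | Protocol 10.3.4 | Attended events, and unattended events that worry the parent |
| Which events are left to the interview? | Protocol 10.3.4 | Events that are neither |
| Must these be recorded? | Protocol 10.3.6, 10.3.10 | Yes, including grade 1 |
| What does the example question ask for? | Protocol 8.3.2 | Only significant problems |
| Is there a symptom list behind it? | Protocol 8.3.2 | No; staff are advised against one |

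Rows 2 and 3 require collection of events that row 4 does not ask about. The passages are inconsistent wherever the example is used as printed.

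**Which outputs are exposed**

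- Not affected: events solicited by eDiary within their solicited periods. These are injection-site pain, redness and swelling, drowsiness and loss of appetite over Days 1-4, and fever and rashes over Days 1-43 (protocol 10.3.3, 10.3.10).
- Unlikely to be affected: SAEs, which a parent would regard as significant.
- Exposed: other unsolicited events in Days 1-43, chiefly mild ones.

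**Illustration**

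Let *p* be the true percentage with any unsolicited AE, *m* the share of those children who had only minor unattended events, and *s* the share of those minor-only children missed because of the wording. All three are assumptions.

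Recorded percentage = *p* × (1 − *m* × *s*)

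With *p* = 30% and *m* = 0.50:

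- *s* = 0: 30 × (1 − 0) = 30.0%
- *s* = 0.25: 30 × (1 − 0.125) = 26.25%, or 26.3% rounded
- *s* = 0.50: 30 × (1 − 0.25) = 22.5%
- *s* = 1: 30 × (1 − 0.50) = 15.0%

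The loss in percentage points is *p* × *m* × *s*. Over *p* from 20% to 50% and *m* from 0.3 to 0.7:

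- *s* = 0: no loss.
- *s* = 0.25: from 20 × 0.3 × 0.25 = 1.5 to 50 × 0.7 × 0.25 = 8.75 points.
- *s* = 0.50: from 20 × 0.3 × 0.5 = 3.0 to 50 × 0.7 × 0.5 = 17.5 points.

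The direction is downward whenever *s* exceeds zero. The documents do not show whether it does.

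**The case against.** The strongest reply is that this is one illustrative sentence in a protocol with several other ways of finding minor events.

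- The question is introduced as an example of a preferred method. It is not a mandatory script, and staff remain free to ask a further open question. This stands, and it is why the finding is a risk only.
- Parents are told to report all kinds of symptoms. This helps, and it carries no severity filter. It addresses the kind of symptom, though, and does not say that minor events count.
- At each visit or contact the parent is asked about every medication and product taken (protocol section 6.8). This can bring out minor illnesses that were treated, but not those left untreated.
- Medical records are reviewed at the next visit. An event that was never medically attended seldom leaves a record, so this route is weak here.
- Nonserious AEs are recorded at Day 1, Day 2-3, Day 15 and Day 43 (protocol section 1.3, Table 3), so parents are asked repeatedly. This aids recall, but the filter recurs if the same question is used each time.
- Section 4.1 places a guide script for the Day 2-3 and Day 181 calls in the Study Reference Manual, which is not available here. Its wording may already be neutral.

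A reader might also infer that the loss differs between groups because site staff know the vaccine given (protocol section 6.3.4). The documents do not support attributing that to this wording. The parent judges what is significant, and parents are blinded under the Appendix 4 glossary. Staff have no rule that lets them screen out minor events. Any influence of unblinded staff comes from the single-blind design and would remain after rewording. The SAP plans no statistical comparison of safety between groups (section 16).

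**Conclusion.** The inconsistency within the protocol is real: the example asks for less than sections 10.3.4, 10.3.6 and 10.3.10 require to be collected. Where sites use it, minor unsolicited AEs may be under-collected, and the Day 1-43 percentage is at risk of downward bias of unknown size. This rests on two assumptions: that some sites use the question as printed, and that the partial back-ups do not recover every minor event.

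Two stronger readings are tempting. One is that the percentage is in fact understated. The documents give no rate or capture figure, and the question is not binding, so zero loss remains possible. The other is that nothing recovers the missed events. The instruction to parents, the medication question, the records review and the repeated contacts can each recover some. The percentages in the working show only how a loss would carry through to the endpoint; they do not estimate it for this trial.

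**What to change.** In protocol section 8.3.2, replace the example with a neutral question that has no severity filter, such as: *Has your child had any health problem, however minor, since the last visit or contact?* Use the same wording in all groups and keep the advice against checklists. Check the telephone script in the Study Reference Manual and align it if it carries the same filter. If collection has already finished, describe the wording as a limitation of the unsolicited AE percentages in the clinical study report.

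The cost is one sentence in the protocol and possibly one in the manual. More minor events would be recorded and coded, and the AE percentages may look slightly higher. Sample size, endpoints and analyses do not change.
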